#### **4.6 Subsequent Therapy**

All subjects who leave the study – be it prematurely or per protocol – will continue with the DM-related treatment they had before study participation, or with another standard of care at the discretion of the investigator.

## 5 INVESTIGATIONAL MEDICINAL PRODUCT(S)

### 5.1 Characterisation of Investigational Product(s)

Name of Medicinal Product: *octanorm*

Active ingredient of *octanorm*: Human normal immunoglobulin

The biochemical characteristics of the product are displayed in Table 4.

**Table 4: Biochemical Characteristics of *octanorm***

Parameter	
Total protein (of which $\geq 96\%$ or $\geq 95\%$ is human IgG, depending on regulatory requirements)	150 – 180 mg per mL
Maltose	70 – 90 mg per mL
Octoxynol	$\leq 5$ $\mu$ g per mL
TNBP	$\leq 1$ $\mu$ g per mL
IgA	$\leq 0.6$ mg per mL
Polysorbate 80	25 – 60 $\mu$ g per mL
pH	5.0 – 5.8
Osmolality	310 – 380 mosmol/kg
Polymers + Aggregates	$\leq 5\%$ of the total chromatogram area
Monomers + Dimers	$\geq 90\%$ of the total chromatogram area
Fragments	$\leq 5\%$ of the total chromatogram area
Sodium	$\leq 30$ mMol/L

*octanorm* is a sterile solution of human normal immunoglobulin containing 16.5% (165 mg/mL) protein. Each batch (lot) of *octanorm* is prepared from at least 3,500 donations of human fresh frozen plasma. Effective viral reduction is obtained via a combination of 3 validated manufacturing steps: cold-ethanol fractionation, solvent/detergent treatment with TNBP and Octoxynol, and pH 4 treatment. The manufacture of *octanorm* is based on the *Octagam* manufacturing process including an additional adsorption step onto commercially available and widely used chromatography column for the removal of coagulation factor XI. The process is identical up to the step of diafiltration. After this step the product solution is concentrated to a target concentration of 200 g/L. Polysorbate 80 and maltose are added during final formulation to final concentrations of 25-60  $\mu$ g/mL and 70-90 mg/mL, respectively.

The efficacy of the virus inactivation / removal procedures has been extensively validated according to relevant international guidelines. Further information can be found in the Investigators' Brochure.

For placebo, 0.9% sodium chloride solution will be used.

## 5.2 Packaging and Labelling

Each vial will be labelled as given in the following master labels:

### US Master Label – Open label octanorm:

**Caution: New Drug-Limited by Federal (or United States) law to investigational use**

**Octanorm 16.5%**

Study: **SCGAM-02**

Unit size: \_\_\_\_\_ mL

1 mL contains 165 mg protein of which  $\geq$  96% is human normal immunoglobulin.

Solution for subcutaneous injection.

To be stored at +2°C (36°F) to +8°C (46°F) and protected from light. Must not be frozen.  
Must be inspected visually for particulate matter and discoloration prior to administration.

Do not use non-homogenous solutions or those that have a deposit.

To be warmed up to room or body temperature before use.

Dosage: please refer to the handling instruction provided.

Keep out of reach of children.

Patient no.: \_\_\_\_\_

Infusion Cycle: \_\_\_\_\_

Batch no.: \_\_\_\_\_

Infusion Session: \_\_\_\_\_

Expiration date: \_\_\_\_\_

Sponsor: OCTAPHARMA Pharmazeutika Produktionsges.m.b.H., [name], Tel: [REDACTED]

### EU Master Label – Open label octanorm:

**FOR CLINICAL TRIAL USE ONLY**

Study: **SCGAM-02**

Unit size: \_\_\_\_\_ mL

**Octanorm 16.5%**

1 mL contains 165 mg protein of which  $\geq$  95% is human normal immunoglobulin.

Solution for subcutaneous injection.

To be stored at +2°C to +8°C and protected from light. Must not be frozen.

Must be inspected visually for particulate matter and discoloration prior to administration.

Do not use non-homogenous solutions or those that have a deposit.

To be warmed up to room or body temperature before use.

Dosage: please refer to the handling instruction provided.

Keep out of reach of children.

Patient no.: \_\_\_\_\_

Infusion Cycle: \_\_\_\_\_

Batch no.: \_\_\_\_\_

Infusion Session: \_\_\_\_\_

Expiration date: \_\_\_\_\_

Investigator:

Sponsor: OCTAPHARMA Pharmazeutika Produktionsges.m.b.H., [name], Tel: [REDACTED]

**US Master Label – Open label placebo:**

**Caution: New Drug-Limited by Federal (or United States) law to investigational use**  
Study: **SCGAM-02**  
**Sodium Chloride 0.9% w/v solution**  
Unit size: \_\_\_\_\_ mL  
Sterile solution for subcutaneous injection  
1000 mL of solution contain  
Sodium chloride 9.00 g  
Electrolyte concentrations mmol per 1000 mL (approx):  
Sodium 154 mmol  
Chloride 154 mmol  
Do not store above +25°C (+77°F) [depending on product purchased]. Do not freeze.  
Only to be used if solution is clear and container undamaged.  
Dosage: please refer to the handling instruction provided.  
Patient no.: \_\_\_\_\_ Infusion Cycle: \_\_\_\_\_  
Batch no.: \_\_\_\_\_ Infusion Session: \_\_\_\_\_  
Expiration date: \_\_\_\_\_  
Sponsor: OCTAPHARMA Pharmazeutika Produktionsges.m.b.H., [name], Tel: [REDACTED]

**EU Master Label – Open label placebo:**

**FOR CLINICAL TRIAL USE ONLY**  
Study: **SCGAM-02**  
**Sodium Chloride 0.9% w/v solution**  
Unit size: \_\_\_\_\_ mL  
Sterile solution for subcutaneous injection  
1000 mL of solution contain  
Sodium chloride 9.00 g  
Electrolyte concentrations mmol per 1000 mL (approx):  
Sodium 154 mmol  
Chloride 154 mmol  
Do not store above +25°C [depending on product purchased]. Do not freeze.  
Only to be used if solution is clear and container undamaged.  
Dosage: please refer to the handling instruction provided.  
Patient no.: \_\_\_\_\_ Infusion Cycle: \_\_\_\_\_  
Batch no.: \_\_\_\_\_ Infusion Session: \_\_\_\_\_  
Expiration date: \_\_\_\_\_  
Investigator: \_\_\_\_\_  
Sponsor: OCTAPHARMA Pharmazeutika Produktionsges.m.b.H., [name], Tel: [REDACTED]

Final labelling will comply with the national requirements of each country where the study is to be conducted. Blinded labels for syringes will be provided.

### **5.3 Conditions for Storage and Use**

*octanorm* 16.5% must be stored and transported light-protected at 2 °C to +8 °C (36 °F to 46 °F) and must not be frozen. *octanorm* 16.5% must not be used after its expiration date.

Sodium chloride 0.9% solution should be stored and transported according to its product information. Conditions will be stated on the IMP label.

The authorised personnel at the site will ensure that the IMP is stored in appropriate conditions with restricted access and in compliance with national regulations.

#### **5.4 Dose and Dosing Schedule**

*octanorm 16.5%* is available in vials with different volumes of solution 12 mL (2 grams) or 48 mL (8 grams). Vials of different volume should be combined in order to reach the required volume of amount of IgG.

Subjects are randomly assigned to *octanorm 16.5%* 0.5 g/kg/week or to placebo (0.9% sodium chloride solution).

If a subject is randomized to receive placebo (0.9% sodium chloride solution), the same volume with the same infusion rate as would have been applied in case the subject would have been randomized to 0.5 g/kg *octanorm 16.5%* will be used.

Body weight is to be measured prior to the first IMP administration and reported to the IRT as it is needed for the calculation of the required IMP dose. Body weight is also to be measured at Visit 5 Week 12, and Visit 8 Week 24. These weight measurements are to be reported to the IRT and will be used by IRT for IMP dose adjustment.

*octanorm* or placebo has to be administered subcutaneously every week ( $\pm 2$  days).

A minimum interval of 4 days must be kept in between two consecutive subcutaneous infusion cycles.

#### **5.5 Preparation and Method of Administration**

Vials of *octanorm* or placebo must be allowed to warm to room or body temperature prior to infusion. Thereafter, *octanorm* or placebo should be infused subcutaneously using a syringe driver for precise infusion rates and standard infusion materials provided to the patients by the site. The correct amount of solution taken from 12 or 48 mL vials of *octanorm* or placebo containers will be infused with the aid of a syringe driver.

The content of the vials/containers will have to be transferred into the syringes suitable for the syringe driver selected.

*octanorm* or placebo must not be mixed with other medicinal products. An aseptic technique must be used throughout the procedure.

Each vial of *octanorm* must be examined visually by unblinded site personnel and if administered at home by the unblinded home healthcare nurse for particulate matter and discoloration prior to administration. The solution should be clear or slightly opalescent. Solutions that are cloudy or have a deposit must not be used. The same procedures should also be performed for 0.9% sodium chloride solution.

The mobile healthcare research nurses will be instructed in the use of the following:

- syringe driver,
- infusion techniques,
- aseptic technique,
- document completion and

- measures to be taken in case of severe AEs.

Patients will be instructed in keeping of a patient diary and measures to be taken in case of severe AEs. During the first four weeks (first 4 infusion cycles), all infusions will be administered at the study site. Apart from Visit 3, where at least the first session of an infusion cycle will also be administered at the site, the next two weeks can be performed either at the patient's home by the mobile healthcare research nurses or at the site (decision to be taken by Investigator and patient based on previous experience). Thereafter, SCIG infusions will be administered at home by mobile healthcare research nurses, apart from Visits 4-9, where at least the first session of an infusion cycle will be administered at the site. Based on the Investigator's decision a home infusion can be replaced with an on-site infusion if considered medically relevant. Investigator's decision should be documented in this case in patient's source documents.

Patients must be monitored at the study site for one hour after the infusion of *octanorm* or placebo.

*octanorm* or placebo (see below) has to be administered subcutaneously every week ( $\pm 2$  days) using a syringe driver for precise infusion rates. The total dose/volume of a weekly infusion will be calculated on the basis of the body weight. The weekly infusion will be performed in two separate sessions (= 1 infusion cycle for a given weekly administration). An infusion cycle comprises both sessions to be administered on 1 or 2 days, either on the same day or on two consecutive days or with maximum one day in between two sessions.

Infusion sites: Up to 6 injection sites and up to 2 syringe drivers can be used simultaneously in one session. In case the allowed flow rate cannot be reached with the 2 syringe drivers because of currently approved/available syringe drivers in the particular country – up to 4 syringe drivers can be used, although the number of simultaneous injection sites remains maximum 6. Up to 12 injection sites can be used consecutively during a single session. Injection sites should be at least 2 inches (approx. 5 cm) apart. The actual sites of injection should be changed with each administration.

Volume per injection site: In the first two weeks (infusion cycles 1-2), 20 mL per injection site should not be exceeded. In the next two weeks (infusion cycles 3-4), max. 25 mL per injection site are permitted. In infusion cycles 5 – 12, this may gradually be increased to 35 mL/site. Starting with infusion cycle 13 and when the previous volumes were well tolerated, increases of  $\leq 10$  mL/site per infusion cycle can be made up to a maximum of 60 mL/site.

Infusion rate: The initial flow rate in the first two weeks is 20 mL per hour per site. For subsequent infusions, the flow rate may gradually be increased to a maximum of 30 mL/hr/site as tolerated. The maximum flow rate for all sites combined should not exceed a total of 180 mL per hour.

## 5.6 Blinding, Emergency Envelopes, and Breaking the Study Blind

To maintain blinding, the unblinded pharmacist or designee will receive and prepare IMP. IMP will be prepared and infused in a manner that will blind the Investigator and other blinded personnel to the study treatment. Unblinded personnel must not communicate to the Investigator or other blinded site personnel which product was assigned to the subject. The total dose and required volume will be calculated on the basis of the bodyweight. Subjects randomized to receive placebo will receive the same volume as if the subject would have been

randomized to 0.5 g/kg *octanorm* 16.5%. IMP preparation during home treatments will be performed by unblinded mobile research nurses.

The subject and blinded study personnel will remain blinded with respect to study treatment throughout the entire 32 week treatment period.

To further assure the double-blind character of this study, the Investigator or designee who applies and provides the medication to the subject will not be involved in any evaluations other than drawing blood samples or checking for vital signs, i.e. will not be involved in any subject ratings (e.g. CSM, CDASI).

The Investigators will be provided with an unblinding procedure to disclose the actual treatment of a particular subject in case of medical emergency; this can be a sealed envelope or its electronic equivalence.

Blinding should only be broken under the following circumstances:

- Occurrence of serious and presumably related AEs but only if the Investigator needs to know the assigned treatment for a proper clinical management of the subject.
- If unblinding is required by the local regulatory authorities.

Whenever possible, the Investigator should notify the Sponsor prior to unblinding. However, the decision and the responsibility to break the blind in emergency situations resides solely with the investigator. In the event of medical emergency to keep subject safety, the investigator will be able to unblind a patient immediately without needing to contact any third party.

In order to maintain the blind, IgG plasma level results performed at the central laboratory will not be revealed to the Sponsor, the Investigator and other blinded personnel at the study site.

## **5.7 Treatment Compliance**

### **5.7.1 Drug Dispensing and Accountability**

Any IMP provided to the site will be accounted for. This includes IMP received at the site and IMP dispensed to patients.

*octanorm* or placebo will be delivered to the participating sites by the Sponsor or designee.

A Drug Inventory and Dispensing Log will be kept current by the pharmacist or designee, detailing the dates and quantities of IMP received and dispensed to each subject/patient and the remaining quantity. The inventory and dispensing log will be available to the unblinded monitor to verify drug accountability during the study.

Unused IMP can be destroyed at the study site or returned to the Sponsor for destruction. Destruction can be initiated only after accountability has been verified and fully reconciled by the unblinded monitor and after the Sponsor has granted written approval of destruction. Empty or partially used vials should be destroyed at the study site or at the pharmacy following local policies.

### **5.7.2 Assessment of Treatment Compliance**

Patients will receive all subcutaneous infusions either at the study site by authorized study personnel or by mobile healthcare research nurses at home.

Throughout the study, mobile healthcare research nurses will be asked to document the dates of home treatment, batch numbers, number of vials, volume and speed of infusion, number and location of injection site(s). Infusion details for infusions administered at the study site will be documented at the study site.

Property of Octapharma. Do not copy or distribute without written permission.

## 6 STUDY CONDUCT

Subjects have to be informed about the study details and have to give their written informed consent. A full written informed consent must be available before the start of any screening activities.

The flowchart of assessments by study visit is shown in **Table 1**.

Prior to treatment initiation, subjects will have to be screened for eligibility (inclusion and exclusion criteria).

If feasible, screening should be completed within 2 weeks. However, screening results should be available as soon as possible. Based on the screening results, the subjects' eligibility for the study is determined. The Baseline Visit is to be performed 4 weeks (+/- 4 days) after the last pre-study IGIV treatment.

For Screening failures, the reason for screen failure and demographic information will be entered into the eCRF.

### 6.1 Observations by Visit

#### 6.1.1 Screening Visit (Visit 1; duration up to 14 days, i.e. Week -2 to 0)

The following assessments will be performed during the Screening Visit:

- Obtaining voluntarily given, written (signed and dated) informed consent.
- Demographic and baseline characteristics.
- Medical history and prior/concomitant therapy.
- Physical examination.
- Vital signs (including body weight and height).
- Standard ECG.
- Blood samples for safety laboratory (hematology and clinical chemistry).
- Blood samples for enzymes.
- Blood sample for biomarkers of disease activity.
- Pregnancy test (in WOCBP).
- CSM.
- Wells probability score for deep vein thrombosis (DVT).
- Wells probability score for pulmonary embolism (PE).
- Inclusion and exclusion criteria.
- Visit registration in IRT.

For patients from Study GAM10-08:

- SCGAM-02 Informed consent to be provided to patient before GAM10-08 Week 40 visit.

### 6.1.2 Visit 2 (Week 0; Baseline)

Subjects who are eligible will visit the study site and enter the treatment period after randomization.

Visit 2 should take place within 2 weeks after the Screening Visit. The Baseline Visit is to be performed 4 weeks (+/- 4 days) after the last pre-study IGIV treatment.

All eligible subjects will receive their first infusion session of either 0.5 g/kg *octanorm 16.5%* or placebo as per randomization. The following assessments will be performed:

#### Before infusion:

- Randomization and enrolment.
- SF-36v2.
- Physical examination.
- Vital signs and body weight.
- Blood sample for safety laboratory (hematology and clinical chemistry).
- Blood sample for additional safety lab parameters (serum haptoglobin and plasma-free hemoglobin)
- Direct Coombs' test (if positive, the antibodies responsible for the positive Coombs' test will be eluted to investigate their specificity (anti-A, anti-B or anti-D)).
- Urinalysis.
- Blood sample for serum IgG.
- Blood samples for enzymes.
- Blood sample for viral markers.
- Blood sample for D-dimers.
- CSM.
- CDASI.
- Visit registration in IRT.

#### During and after the infusion session:

- Administration/Infusion of IMP.
- Vital signs at least once during and 1 hour (+/- 10 min) after the end of the infusion session.

#### At least 1 hour after the infusion session:

- Wells probability score for DVT. If score is likely for DVT ( $\geq 2$  points), perform Doppler scan and take blood sample for D-dimers.
- Wells probability score for PE.
- Assessment of local injection site reactions.

In addition, AEs will be monitored and concomitant therapy will be documented.

The second session of the infusion cycle will be administered either on the same day or on two consecutive days or with maximum one day in between two sessions.

During the first four weeks (first 4 infusion cycles), all infusion sessions will be administered at the study site.

For patients from Study GAM10-08:

- GAM10-08 Week 40 Termination Visit will be SCGAM-02 Baseline Visit. GAM10-08 Week 40 test results will be used for SCGAM-02 Baseline Visit evaluations and subjects who are eligible will be randomized and will receive their first SCGAM-02 infusion at the day of the GAM10-08 Week 40 Termination Visit.

### 6.1.3 Visit 3 (Week 4)

At least the first session of the infusion cycle needs to be administered at the site. The following assessments will be performed:

#### Before the infusion session:

- Patient diary check.
- Physical examination.
- Vital signs.
- Blood sample for safety laboratory (hematology and clinical chemistry). If hemoglobin is found to have decreased by  $\geq 2$  g/dL from baseline, the additional safety laboratory parameters (serum haptoglobin, plasma-free hemoglobin) and Direct Coombs' test will be performed as well.
- Blood sample for serum IgG.
- Blood samples for enzymes.
- CSM.
- CDASI.
- Visit registration in IRT.

#### During and after the infusion session:

- Administration/Infusion of IMP.
- Vital signs at least once during and 1 hour (+/- 10 min) after the end of the infusion session.

#### At least 1 hour after the infusion session:

- Wells probability score for DVT. If score is likely for DVT ( $\geq 2$  points), perform Doppler scan and take blood sample for D-dimers.
- Wells probability score for PE.
- Assessment of local injection site reactions.

In addition, AEs will be monitored and concomitant therapy will be documented.

Apart from this visit, the fifth and sixth infusion cycle can be performed either at the patient's home by the mobile healthcare research nurses or at the site (decision to be taken by Investigator and patient based on previous experience). Thereafter, SCIG infusions will be administered at home by mobile healthcare research nurses, apart from Visits 4-9, where at least the first session of an infusion cycle will be administered at the site. Based on the

Investigator's decision a home infusion can be replaced with an on-site infusion if considered medically relevant.

Home visits:

To ensure blinding of the patient, SCIG infusions at home will always be administered by mobile healthcare research nurses who are obliged to keep patients blinded during home infusions.

The following assessments will be performed by research nurse:

Before the infusion session:

- Patient diary check for completeness
- Review of adverse events and concomitant medication changes. All new AEs and concomitant medication changes are to be documented by patient in the patient's diary.
- Contact Investigator to discuss patient's safety or IMP administration, if necessary

Preparation and administration of IMP

After the infusion session:

- Notify site staff about completed infusion session
- Schedule the next home visit

Patient has to take temperature 1 hour after the end of the infusion

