#### 3.2 Overall Study Design and Plan

This study is planned to start in Q3 2018 and to be completed by Q2 2020, resulting in an overall duration of 24 months.

It will be a double-blind, randomized, placebo-controlled, parallel group, multicenter, comparative efficacy and safety study in a minimum of 78 adult subjects of both genders with

[figure not shown]
definite or probable DM according to the criteria of Bohan and Peter [29, 30] who have previously responded to IGIV therapy.

As DM is a rare disease, about 45 sites are projected to participate in countries worldwide with emphasis on European countries and North America.

Subjects eligible after screening will be randomized 1:1 to receiving up to 32 infusion cycles of either *octanorm* 0.5 g/kg/week or placebo every week for 32 weeks. The weekly infusion will be performed in two separate sessions (= 1 infusion cycle for a given weekly administration). An infusion cycle comprises both sessions to be administered on 1 or 2 days, either on the same day or on two consecutive days or with maximum one day in between two sessions.

In case of clinically important deterioration (for definition see Section 4.3.1) during the SC treatment period, subjects will be discontinued from the study, will undergo a termination visit and may optionally receive Octagam 10% as IGIV rescue medication (2g/kg BW one time, provided by the sponsor) or rescue treatment according to standard of care at the site by the treating physician. Octagam 10% or any other commercially available IGIV as optional IGIV rescue medication can be also reimbursed by the sponsor (2g/kg BW one time). IGIV as rescue medication should be administered with infusion rate not higher than 0.04 mL/kg/min (240 mg/kg/h).

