#### 7.3.2.2 Collection of AEs

The condition of the subject/patient will be monitored throughout the study. At each visit, whether scheduled or unscheduled, AEs will be elicited using a standard non-leading question such as "How have you been since the last visit/during the previous study period?" AEs should be registered starting from the first dose of IMP (start of first injection).

In addition, the Investigator will check the subject/patient diaries (if applicable) for any documented event.

Local injection site reactions are to be assessed by both patients and investigators.

Patients have to grade the overall perception of local reactions in their diaries at 24 hours ( $\pm 3$  hours) post-infusion session using a 4-point rating scale: 0=none, 1=mild, 2=moderate, 3=severe.

Investigators have to evaluate local reactions at approximately 1 hour post-infusion session at every study site visit, using the same 4-point rating scale: 0=none, 1=mild, 2=moderate, 3=severe.

Local infusion site reactions will be noted on the adverse event pages in the CRF.

Any AE or ADR occurring during the study will be noted in detail on the appropriate pages of the eCRF. If the subject reports several signs or symptoms representing a single syndrome or diagnosis, the diagnosis should be recorded in the eCRF. The Investigator will grade the severity of all AEs or ADRs (mild, moderate, or severe), the seriousness (non-serious or serious), and the causality as defined in **Sections 7.3.2.3, 7.3.2.4, and 7.3.3**. The Sponsor is responsible for assessing the expectedness of each ADR (expected or unexpected) as defined in **Section 7.3.2.5**.

In the event of clinically significant abnormal laboratory findings, the tests will be confirmed and the patient followed up until the laboratory values have returned to normal and/or an adequate explanation for the abnormality has become available.

Diseases, signs and symptoms, and/or laboratory abnormalities already present before the first administration of IMP will not be considered AEs unless an exacerbation in intensity or frequency (worsening) occurs.

The Investigator will provide detailed information about any abnormalities and about the nature of and reasons for any action taken as well as any other observations or comments that may be useful for the interpretation and understanding of an AE or ADR.

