11.1. Adverse Events

All reported AEs will be coded according to MedDRA.

An AE is defined as treatment-emergent, if first onset or worsening is during the treatment period. Only treatment-emergent AEs (TEAEs) are accounted for in the analysis.

For each TEAE, the exact time of onset will be recorded. A TEAE will be classified as infusional AE if the onset is during the first infusion session of a given infusion cycle, between the two infusion sessions of the same cycle, or within 72 hours after the end of the 2nd infusion session of the same infusion cycle.

All reported events will be listed and tabulated in full detail; in particular the following key figures will be presented:

- Total incidence and number of TEAEs reported by severity and overall
- Incidence and number of related TEAEs by severity and overall
- Incidence and number of TEEs and HTRs
- Incidence and number of SAEs
- Incidence and number of TEAEs leading to withdrawal
- Incidence and number of infusional AEs by severity and overall
- Number of infusion cycles with infusional AEs

Narratives will be prepared describing each death, other SAEs, and other significant AEs that are judged to be of special interest because of clinical importance, including all TEEs and HTRs reported.

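### At home infusions the unblinded nurse who gives the product also reviews adverse events, and Protocol Sections 5.6 and 6.1.3 need to be reconciled on whether that is allowed

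*Protocol*

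**What the plan says.** **Who gives the product at home.** Protocol Section 5.6 states: "IMP preparation during home treatments will be performed by unblinded mobile research nurses". Section 5.5 also describes the home nurse who inspects the vials as unblinded. Section 6.1.3 (Home visits) has the mobile nurse prepare and give the infusion and obliges the nurse to keep the patient blinded.

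**What that nurse assesses.** The list of nurse assessments before each home session in Section 6.1.3 includes a check that the diary is complete, then "Review of adverse events and concomitant medication changes", then "Contact Investigator to discuss patient's safety or IMP administration, if necessary". The AE item adds that the patient enters new events and medication changes in the diary.

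**What infusion staff may assess.** Section 5.6 says that the investigator or designee who applies the medication "will not be involved in any evaluations other than drawing blood samples or checking for vital signs". The same sentence goes on to explain this as having no part in subject ratings, with the core set measures (CSM) and CDASI as examples.

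**How AEs are otherwise collected.** Under Section 7.3.2.2, at each visit, scheduled or not, "AEs will be elicited using a standard non-leading question such as" one asking how the patient has been. The investigator also checks the diary and grades severity, seriousness and causality. Patients grade local reactions themselves 24 hours after a session; investigators grade them at site visits.

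**What is reported.** SAP Section 11.1 tabulates, among others, "Incidence and number of related TEAEs by severity and overall", together with all treatment-emergent AEs (TEAEs) and infusional AEs. SAP Section 11.2 compares local injection site reactions by treatment group.

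**The concern.** A double-blind trial protects its harm comparison by keeping people who know the arm out of the steps that decide which events are noticed and passed on. Here the plan gives one of those steps to someone who knows the arm. Before each home session the nurse reviews AEs with the patient and judges whether the investigator needs to hear about a safety matter before the next site visit. Section 6.1.3 provides no script for the review and no criterion for the contact.

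Many of the events at stake are subjective, such as headache, fatigue and site discomfort. A nurse who knows the syringe holds immunoglobulin could ask about these more readily than with saline, or could discount them as expected. Either would make recorded AE frequencies depend partly on arm knowledge. SAP Section 11.1 extends the infusional-AE window to 72 hours after the second session of a cycle. For cycles given at home, that window mostly falls outside site visits.

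**Working it through.** The plan gives no home share of infusions, so there is no stated figure to reproduce. The share follows from the schedule.

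**1. Total sessions.** Protocol Section 3.2: "Subjects eligible after screening will be randomized 1:1 to receiving up to 32 infusion cycles", and "The weekly infusion will be performed in two separate sessions (= 1 infusion cycle for a given weekly administration". So 32 × 2 = 64 sessions for a patient who completes treatment.

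**2. Sessions on site.** From Protocol Sections 6.1.2 to 6.1.9:
- Cycles 1-4: all on site, 4 × 2 = 8.
- Visit 3 (cycle 5): at least the first session, 1.
- Visits 4-9: at least the first session at each, 6; both sessions, 12.
- Cycles 5-6: home or site by choice, apart from the first session of cycle 5.

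**3. Home sessions = 64 − on-site sessions.**
- Most at home: 64 − 8 − 1 − 6 = 49; 49/64 = 76.6%.
- Cycles 5-6 on site, only first sessions at Visits 4-9 on site: 64 − 8 − 4 − 6 = 46; 71.9%.
- Cycles 5-6 at home where allowed, both sessions at Visits 3-9 on site: 64 − 8 − 14 = 42; 65.6%.
- Cycles 5-6 and both sessions at Visits 4-9 on site: 64 − 8 − 4 − 12 = 40; 62.5%.

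Section 6.1.3 names cycles 5 and 6 as the optional ones. Section 3.3.1 speaks only of the two weeks following, apart from Visit 3. If that means cycles 6-7, the low case is 64 − 8 − 2 (cycle 5) − 4 (cycles 6-7) − 12 = 38; 59.4%. The high case stays at 49.

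None of the low cases is a floor. The investigator may move a home infusion to the site if medically relevant, and a patient who stops early has a larger on-site share.

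**4. Sections 5.6 and 6.1.3 side by side.**
- The first clause of the 5.6 sentence covers any evaluation and exempts two activities. AE review is neither of them, and Section 6.1.3 classes it as an assessment. On this clause alone the sections conflict.
- The second clause narrows the meaning to subject ratings and names efficacy instruments. On this clause AE review may be outside the bar.
- The two exemptions would hardly be needed if only efficacy ratings were meant, so the narrow reading does not settle the matter.

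**5. Where arm knowledge can enter.** The chain from event to table is: the patient notices; the patient writes the diary (blinded); the nurse reviews and may contact the investigator (unblinded); the investigator elicits, checks the diary and grades (blinded). The one unblinded link can affect what is prompted into the diary and what reaches the investigator between 4-weekly visits. It assigns no grade, causality or eCRF entry.

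**The case against.** The strongest reply is that the sponsor has already contained the problem. The 5.6 restriction is explained as being about ratings such as CSM and CDASI. The blinded patient makes the home record, and the investigator asks the non-leading question, checks the diary and grades every event. Section 4.2.1 bars the nurses from making therapy assignments. Safety analysis is descriptive, suspected intravascular hemolysis uses laboratory criteria, and causality of thromboembolic and hemolytic events is assessed blind by investigator, sponsor and IDMC. Section 7.3.2.2 also speaks of each visit, and Section 6.1.3 calls these contacts home visits, so the non-leading rule may already apply there.

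Most of this stands, and it rules out several stronger readings that a reader might infer:

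- *That 5.6 plainly forbids the nurse's AE review.* The explanatory clause prevents that; the text is ambiguous.
- *That patient blinding and non-disclosure are the only safeguards.* Diary entry by the patient and the investigator's elicitation, diary check and grading are also in place.
- *That the home share measures the bias.* It counts sessions, not events ascertained only through the nurse. An assumed 10% to 20% relative change in detection on octanorm at home would give a TEAE rate ratio from 1 + 0.625 × 0.10 = 1.06 to 1 + 0.766 × 0.20 = 1.15 under equal true rates. But the detection change has no source in the documents, its direction is unknown, and the formula assumes a uniform AE rate per session and no recapture at site visits.
- *That the primary endpoint is compromised.* SAP Section 10.1 counts withdrawal or rescue for any reason as failure, so unequal escalation could in principle reach it. But withdrawal is decided by the patient or the investigator, and the efficacy ratings are made at site visits by staff who do not give the product.

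The reply does not remove the unscripted review and the undefined contact criterion. If the non-leading rule does apply at home, the person eliciting AEs there is unblinded, which is a further reason to fix the wording of the question.

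**Conclusion.** The point holds in a limited form. The protocol gives an arm-aware nurse a stated role in AE ascertainment at home infusions, and Sections 5.6 and 6.1.3 do not make clear whether this is permitted. They need to be reconciled. The role covers about 40 to 49 of 64 planned sessions (62.5% to 76.6%), or 38 on the alternative reading of the optional weeks. These counts assume all 32 cycles are given in two sessions with no unplanned move to the site.

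The existing safeguards limit the bias but leave arm-aware prompting and discretionary escalation between 4-weekly visits possible. The documents support neither a size nor a direction for the effect. The correction is worth making because it is cheap and the safety tables compare arms on many subjective events.

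**What to change.** In Protocol Section 6.1.3 (Home visits), replace the nurse's AE and medication review with two steps: check that the diary is complete, and read out word for word the standard non-leading question of Section 7.3.2.2, with the patient writing the answer in their own words. State in Section 7.3.2.2 that it applies to home visits. State in Section 5.6 whether AE review counts as an evaluation, so that the sections agree.

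Keep the nurse's safety contact with the investigator unrestricted, and log each contact. The script should govern routine elicitation only and must not discourage a nurse from raising a safety matter.

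Investigator grading is already in Section 7.3.2.2 and needs no new rule. A supportive safety table by source of report in SAP Section 11.1 is optional and would need one source field.

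The cost is protocol and nurse-instruction wording, a short script and a contact log to maintain. The downside is slightly less probing for minor AEs at home. No extra visits or staff are needed.
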